## ABBREVIATIONS

Abbreviation	Definition
6MWD	6-minute walk distance
6MWT	6-minute walk test
ACTH	adrenocorticotrophic hormone
ALT	alanine aminotransferase
ATC	Anatomical-Therapeutic-Chemical classification
BUN	blood urea nitrogen
CI	confidence interval
CINRG	Cooperative International Neuromuscular Research Group
CK	blood urea nitrogen
CRF	case report form
CTCAE	Common Terminology Criteria for Adverse Events
D/C	discontinuation
DBP	diastolic blood pressure
DMD	Duchenne muscular dystrophy
ECG	electrocardiogram
EK	Egen Klassifikation
FEV1	forced expiratory volume in 1 second
FVC	forced vital capacity
GGT	gamma glutamyl transferase
LOCF	last observation carried forward
LVEF	Left ventricular ejection fraction
MedDRA	Medical Dictionary for Regulatory Activities
mRNA	messenger ribonucleic acid
MMRM	mixed model repeated measures
nmDMD	nonsense mutation Duchenne muscular dystrophy
NSAA	North Star Ambulatory Assessment
PCF	peak cough flow
PEF	peak expiratory flow
SAP	statistical analysis plan
SOC	System Organ Class
SBP	systolic blood pressure
TEAE	treatment-emergent adverse event
TFT	Timed function test
TID	ter in die (3 times per day)
Tx	treatment
UE	upper extremity
ULN	upper limit of normal
WHODRUG	World Health Organization Drug Dictionary
WNL	within normal limits

## 1. OVERVIEW

This statistical analysis plan (SAP) details the statistical methods to be used in the analyses and presentation of the data collected in Study PTC124-GD-020e-DMD, also referred to as Study 020e. Preparation of this SAP incorporates statistical design elements present in the protocol amendment version 2.0 (dated 18 November 2015). Details are documented in sections 1-7.

In addition to the protocol defined analyses, a natural history control using the Cooperative International Neuromuscular Research Group (CINRG) will be utilized in order to help to better understand the long-term ataluren data. Although the planned analysis will not be included in the CSR it will be presented in Section 8 for completeness.

Where conflicts exist between this SAP and the study protocols, the information contained in this SAP supersedes the protocol.

## 2. STUDY DESIGN

All patients who successfully completed the Phase 3 double blind, placebo controlled study (PTC124-GD-020-DMD) were eligible for this Phase 3 open label, extension study (PTC124-GD-020e-DMD). This Phase 3 extension study will evaluate the long term safety of ataluren 10, 10, and 20 mg/kg.

The primary objective of this Phase 3 extension study will be to obtain long-term safety data to augment the overall safety database. The secondary objectives will be to augment the efficacy data collected in the double-blind study (PTC124-GD-020-DMD).

Screening and baseline procedures are structured to avoid a gap in treatment between the double-blind study (PTC124-GD-020-DMD) and this extension study. When possible, Screening/Baseline (Visit 1) for this extension study should occur on the same day as the End-of-Study visit for the double-blind study (PTC124-GD-020-DMD). During the treatment period, study assessments will be performed at clinic visits at Week 12 and thereafter every 12 weeks until the end of the study.

The proposed types and timing of data to be recorded are described in Table 1 for amendment 2.0 (dated 19 November 2015).

**Table 1. Schedule of Events**

Study Period	Screening/ Baseline	Treatment Period											Post-Treatment	
		12	24	36	48	60	72	84	96	108	120	132	144	6 Weeks Post-Tx
Study Week (±7 days)	Day 1	2	3	4	5	6	7	8	9	10	11	12	13	14
Visit	1	2	3	4	5	6	7	8	9	10	11	12	13	14
Informed consent	X													
Vital signs	X a	X	X	X	X	X	X	X	X	X	X	X	X	X
Height	X a	X	X	X	X	X	X	X	X	X	X	X	X	X
Weight	X a	X	X	X	X	X	X	X	X	X	X	X	X	X
Physical examination	X a				X				X				X	
Hematology	X a	X	X	X	X	X	X	X	X	X	X	X	X	X
Biochemistry	X a	X	X	X	X	X	X	X	X	X	X	X	X	X
Urinalysis	X a	X	X	X	X	X	X	X	X	X	X	X	X	X
Renal ultrasound	X a				X				X				X	
12-lead ECG	X a				X				X				X	X
Study drug assignment	X													
Drug Dispensed	X	X	X	X	X	X	X	X	X	X	X	X		
Drug compliance		X	X	X	X	X	X	X	X	X	X	X	X	
Adverse events	X	X	X	X	X	X	X	X	X	X	X	X	X	X
Concomitant medication	X	X	X	X	X	X	X	X	X	X	X	X	X	X
6-minute walk test	X a	X	X	X	X	X	X	X	X	X	X	X	X	
Timed function tests	X a	X	X	X	X	X	X	X	X	X	X	X	X	
North Star Ambulatory Assessment	X a	X	X	X	X	X	X	X	X		X	X	X	
Activities of Daily Living/Disease Status Survey	X a	X	X	X	X	X	X	X	X				X	
PODCI Questionnaire	X a	X	X	X	X	X	X	X	X		X	X	X	
Spirometry	X		X		X		X		X		X		X	
PUL assessment	X	X	X	X	X	X	X	X	X	X	X	X	X	
Pharmacokinetics		X	X	X	X	X	X	X	X	X	X	X	X	

Study procedure need not be performed if Day 1 is within 14 days of the end-of-study evaluations at Week 48 (Visit 8) of the preceding Phase 3 double-blind study (PTC124-GD-020-DMD).

**Abbreviations:**; D/C = discontinuation; ECG = electrocardiogram; F/U = follow-up; PUL = Performance of Upper Limb, Tx = treatment

### **3. STUDY OBJECTIVES AND ENDPOINTS**

#### **3.1. Primary Objective**

The primary objective of this study is to evaluate the long-term safety of ataluren in boys with nonsense mutation dystrophinopathy, as determined by adverse events and laboratory abnormalities.

#### **3.2. Secondary Objectives**

The secondary objectives, which evaluate the effects of ataluren on major clinical manifestations of DMD, are:

##### *Physical*

- To determine the effect of ataluren on ambulation in patients who are ambulatory.
- To evaluate the effect of ataluren on proximal muscle function in patients who are able to perform timed function tests.
- To evaluate the effect of ataluren on physical function in patients who are able to perform the North Star Ambulatory Assessment.
- To evaluate the effect of ataluren on upper limb function.

##### *Pulmonary function*

- To evaluate the effect of ataluren on pulmonary function.

##### *Patient-reported outcomes*

- To determine the effect of ataluren on health-related quality of life (HRQL) as reported by patients and parents/caregivers.
- To assess the effect of ataluren on activities of daily living.

##### *Exposure*

- To assess long-term ataluren plasma exposure.

#### **3.3. Study Endpoints**

##### **Primary:**

- Safety profile characterized by type, frequency, severity, timing, and relationship to ataluren of any adverse events or laboratory abnormalities

##### **Secondary:**

##### **Physical**

- Change in ambulation as measured by the 6MWT
- Change in proximal muscle function as assessed by timed function tests (time to rise from supine position, time to run 10 meters, and time to climb/descend 4 stairs)

- Change in physical function as assessed by the North Star Ambulatory Assessment
- Change in motor performance of the upper limb as measured by the Performance Upper Limb (PUL)

#### **Pulmonary function**

Change in pulmonary function as measured by spirometry (eg. FVC, FEV1)

#### **Patient-Reported Outcomes**

- Change in patient- and parent/caregiver-reported HRQL as measured by the PODCI Transfer/Basic Mobility and Sports/Physical Functioning scores
- Change in patient and parent/caregiver reported activities of daily living

#### **Exposure**

- Pre-dose ataluren plasma concentrations prior to morning ataluren administration at each clinic visit as assessed by a validated bioanalytical method

#### **Safety**

- Change from baseline in other safety parameters (eg, vital signs)

### **3.4. Sample Size**

The sample size for this extension study is not based upon any formal statistical hypothesis, but its upper bound is determined by the requirement that patients must have participated in the previous Phase 3 study of PTC124 (PTC124-GD-020-DMD) in which ~ 220 patients are expected to be enrolled.

## **4. STUDY POPULATION**

- As-Treated population: All subjects who receive at least 1 dose of ataluren treatment in the extension phase. This population will be evaluated in the analyses of safety and efficacy.
- PK population: All subjects who has at least one PK concentration data. This population will used for the PK concentration and parameter summary.

## **5. STATISTICAL ANALYSIS**

### **5.1. General Statistical Considerations**

Summary tables for continuous variables will contain the following statistics: n, mean, standard deviation, standard error, 95% confidence intervals (CIs) on the mean, median, minimum, and maximum. Summary tables for categorical variables will include N, n, and percentages. In by-visit summaries, the analysis visits will be derived via visit mapping windows.

For descriptive summary tables, the all data will be analyzed and displayed by ambulatory status (ambulatory or non-ambulatory) at baseline, unless specified otherwise. Where applicable, the summary data (mean, standard error) will be presented in graphical form of against time of visit.

By-patient listings will be created for each CRF module. The data will be listed by center/subject ID and visit.

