13.2.2. Duration of Therapy

This open-label study is expected to generate at least 144 weeks of safety information. This information will supplement safety data obtained from the randomized, placebo-controlled, double-blind study (PTC124-GD-020-DMD), which has a planned treatment duration of 48 weeks.

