### 5.8.4. Timed Function Tests

Timed function test data (ie, time to stand from supine, time to run/walk 10 meters, time to climb 4 stairs, and time to descend 4 stairs) and change from baseline to each post baseline visit will be summarized descriptively by visit for ambulatory subjects with non-missing baseline timed function tests assessments. Similarly the time to stand from supine, time to run/walk 10 meters, time to climb 4 stairs, and time to descend 4 stairs will also be summarized for each actual age.

Timed function test (TFT) data imputation rules as the following will be used in the summary.

- If time to run/walk 10 meters > 30 sec, then set to 30 sec.
- If time to stand from supine > 30 sec, then set to 30 sec.

The Kaplan-Meier method will be applied to the analysis of age at loss of ambulation. The median age at loss of ambulation will be reported by treatment group in studies 020/020e (ataluren/ataluren, placebo/ ataluren, and overall), corticosteroid use duration (<12 months,  $\geq$ 12 months), and corticosteroid type (deflazacort vs prednisone/prednisolone) at baseline. The Kaplan-Meier curves will also be displayed. The age at loss of ambulation is defined as age of the disease progression reported as the adverse event. The subjects who are ambulatory at the end of study or discontinuation will be censored on the last valid visit date. Age on that date will be used in the analysis.

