### 6.2. Baseline

In general, Baseline is defined as the last non-missing valid assessment prior to or on the date of the first dose of the study. For spirometry tests, Visit 1 measurements can be used as baseline even if they are after the first dose.

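### Apart from age at loss of ambulation, no safety table or by-visit efficacy summary is split by prior Study 020 arm, so boys continuing ataluren and boys coming from placebo are pooled

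*SAP*

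**What the plan says.** Entry to 020e comes from a placebo-controlled parent trial: "All patients who successfully completed the Phase 3 double blind, placebo controlled study (PTC124-GD-020-DMD) were eligible" (SAP 2). Protocol 4.2 requires completion of the Study 020 treatment, "which has a planned treatment duration of 48 weeks" (Protocol 13.2.2).

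SAP 4 defines one as-treated population for safety and efficacy: "All subjects who receive at least 1 dose of ataluren treatment in the extension phase". SAP 5.1 sets the default layout: descriptive data are "displayed by ambulatory status (ambulatory or non-ambulatory) at baseline, unless specified otherwise".

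The one place that keeps the Study 020 arms is SAP 5.8.4, where the median age at loss of ambulation is "reported by treatment group in studies 020/020e (ataluren/ataluren, placebo/ ataluren, and overall"), with Kaplan-Meier curves.

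For change scores, "Baseline is defined as the last non-missing valid assessment prior to or on the date of the first dose of the study" (SAP 6.2). SAP 5.7.1 likewise starts the treatment-emergent period at the first dose taken in this study and ends it 6 weeks after the last. The primary endpoint covers the timing of adverse events and laboratory abnormalities as well as their type and frequency (SAP 3.3).

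**The concern.** At the first 020e dose the two groups of boys are in different states. A boy from the ataluren arm has had about 48 weeks on drug, so his 020e baseline is an on-drug value. A boy from the placebo arm has a post-placebo baseline and starts ataluren on that day. A pooled change from baseline averages two different quantities, and a pooled count of treatment-emergent events mixes first-months exposure with second-year exposure.

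The protocol gives a specific reason to care. In Study 007, mean creatinine, BUN and cystatin C rose slightly and then tended to stabilise early (Protocol 13.2.3 and 14.3). Total cholesterol and triglycerides behaved similarly (Protocol 13.2.6 and 14.3). If that pattern recurs, boys from the ataluren arm enter 020e already on the plateau and only boys from placebo show the rise. The pooled mean would then understate it. A boy whose laboratory grade rose during Study 020 and stayed there would appear in the 020e shift table as unchanged. An event that began on ataluren in Study 020 and continued without worsening is not treatment-emergent in 020e. These are the markers for which the protocol sets up renal and lipid monitoring.

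On efficacy, the secondary aim is to add to the double-blind data (SAP 2). A change from a mixed baseline does not connect to the Study 020 arms.

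**Working it through.** **Step 1: look for a split by prior arm in each SAP section.**

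| SAP section | Split or restriction named | Prior 020 arm? |
|---|---|---|
| 5.2 Disposition, 5.6 Exposure | overall; ambulatory status | no |
| 5.3 Baseline characteristics | overall; corticosteroid duration and type; ambulatory status | no |
| 5.7.1 Adverse events | tables ordered by frequency in the overall group; patient-years summed over all patients | no |
| 5.7.2 Laboratory changes and shifts | none beyond the 5.1 default | no |
| 5.8.1 Vital signs, 5.8.2 ECG | overall subjects | no |
| 5.8.3 6MWT, 5.8.4 timed tests, 5.8.5 NSAA | ambulatory subjects; by visit and by actual age | no |
| 5.8.4 Age at loss of ambulation | 020/020e treatment group; corticosteroid duration and type | **yes** |
| 5.8.6 PODCI, 5.8.7 spirometry, 5.8.8 PUL | by visit; PODCI in ambulatory and PUL in non-ambulatory subjects | no |

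The by-age tables do not use the 020e baseline, so the baseline problem applies to the by-visit change tables and not to them.

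**Step 2: is there a document figure to reproduce?** No. "The sample size for this extension study is not based upon any formal statistical hypothesis", and the only number is a ceiling set by Study 020, "in which ~ 220 patients are expected to be enrolled" (SAP 3.4). The Study 020 allocation ratio is not given.

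**Step 3: illustrate the dilution of an event rate (assumptions only).** Assume all 220 boys enter and prior-placebo boys are between 1/3 and 2/3 of them. As stand-in rates, use Study 007 abdominal pain (Protocol 2.2.3): 12.3% on the low dose for newly exposed boys and 7% on placebo for continuing boys. The true rate in continuing boys is unknown.

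Pooled rate = (n_new × p_new + n_cont × p_cont) / 220. Relative understatement = 1 − pooled / p_new.

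- 73 new, 147 continuing: (73 × 12.3% + 147 × 7%) / 220 = 8.8%, which is 3.5 points or 29% low.
- 110 and 110: 9.65%, which is 2.65 points or 22% low.
- 147 new, 73 continuing: 10.5%, which is 1.8 points or 14% low.

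**Step 4: what a split can and cannot show.**

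- Power to separate 12.3% from 7% (two-sided 0.05) is about 27%, 26% and 20% for the three splits in the same order, so added columns can only be descriptive.
- With no events seen, the 95% upper bound is 1 − 0.05^(1/n). This is 1.35% for n = 220, 2.7% for n = 110, 4.0% for n = 73 and 2.0% for n = 147. The pooled bound of 1.35% does not apply to newly exposed boys alone.

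**The case against.** The case for leaving the plan alone has substance. 020e is a long-term study with no formal hypothesis, and it was stopped early. Early reactions are the business of Study 020, which has a concurrent placebo arm, and 020e is meant to supplement it. A pooled rate is not an error: it correctly describes the population defined in SAP 4. Patient numbers carry over from Study 020 and by-patient listings are planned, so a split could be made later. Finer splits thin the cells, as Step 4 shows. Arm columns alone would not show timing either, because SAP 5.7.1 has no time-to-onset table.

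Most of this stands, and it limits the point to a descriptive addition. It does not remove the point. The first months on ataluren of the boys from placebo are observed only in 020e, the primary endpoint includes timing, and no planned table separates those boys.

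A reader might also infer more than the documents support:

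- **That the randomised contrast is discarded or hidden.** It is not. SAP 5.8.4 keeps it for age at loss of ambulation.
- **That the early-start versus delayed-start comparison is protected by randomisation.** 020e randomises nobody. The contrast is inherited from Study 020 and restricted to boys who completed it, which is selection after randomisation.
- **That exposure is understated by 48 weeks.** SAP 5.6 defines treatment duration within 020e and reports that. Lifetime exposure would be an addition, not a correction.
- **That the boys from placebo are drug-naive.** The Study 020 eligibility criteria are not in these documents.
- **That the dilution is large and known.** Rates of 10% versus 2% at 1:1 would give (10% + 2%) / 2 = 6%, a 40% understatement, but nothing in the documents supports those rates.

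**Conclusion.** The point holds as a reporting gap. The by-visit change tables and the treatment-emergent tables combine two exposure histories with a common restart at 020e entry, so an early-exposure effect or a difference between the two histories cannot be read from them. The direction is dilution of any effect concentrated early in exposure. The amount cannot be derived from the documents: the 14% to 29% range depends on an assumed allocation, full entry of about 220 boys and borrowed Study 007 rates. Nothing here shows that a planned figure is wrong for the population it describes. The point ranks as an inexpensive improvement that should be made, chiefly for the safety tables behind the primary endpoint.

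**What to change.** 1. Add ataluren/ataluren, placebo/ataluren and overall columns, descriptively, to the key treatment-emergent event tables, the laboratory change and shift tables, and the by-visit functional tables. SAP 5.8.4 already uses these groups, so the arm code is available.
2. Add a summary of event onset by time since the first-ever ataluren dose, and cumulative ataluren exposure from that dose. Keep the within-020e duration of SAP 5.6 and label the new figures as a supplement.
3. State in the SAP that the contrast between the two groups is inherited from Study 020, applies to boys who completed that study, and is not a formal test.
4. Keep the overall column, and do not cross every table with ambulatory status.

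The cost is SAP wording, extra table columns, one onset table and linkage to the Study 020 dosing and event dates through the retained patient numbers. No new data are collected from patients. The downside is smaller cells and wider uncertainty in each column.

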## 5.2. Subject Disposition

A summary of subjects who discontinued ataluren treatment prematurely or were removed from the study prematurely will be reported for overall subjects and a subgroup of ambulatory/non-ambulatory subjects at study entry. Reasons for treatment early discontinuations will be described.

Since the sponsor has decided to discontinue the Study 020e, subjects who discontinue the study due to this reason or complete the study per protocol will be considered as censored in the time to discontinuation analysis. The time to discontinuation (in weeks) is calculated as  $(\text{discontinuation date} - \text{first dose date} + 1)/7$  for subjects who discontinue from the study due to reasons other than sponsor's decision of termination the study or transitioning to commercial drug. For subjects who discontinue due to these reasons or complete the study, the censor time is  $(\text{discontinuation date} - \text{first dose date} + 1)/7$  and  $(\text{study completion date} - \text{first dose date} + 1)/7$ , respectively. Time to discontinuation will be assessed using Kaplan-Meier methods and the Kaplan-Meier curve will be displayed.

The protocol deviations will be summarized by type. A listing of protocol deviations will be provided.

## 5.3. Demographic and Baseline Characteristics

Subject demographic and disease characteristics (age, age group (6-11, 12-17, and  $\geq 18$  years), gender, race, ethnicity, height, weight, body mass index, six minute walk distance, six minute walk distance groups ( $<300$  meters,  $\geq 300$ - $<400$  meters,  $\geq 400$  meters), time to run/walk 10 meter, time to stand from supine, time to stand from supine ( $<5s$ ,  $\geq 5s$ ), performance of Upper Limb Assessment (PUL), corticosteroid use (Yes/No), and ambulatory/non-ambulatory) at study entry will be summarized for overall subjects, a subgroup of subjects with corticosteroid use duration ( $<12$  months,  $\geq 12$  months) at baseline, a subgroup of subjects with corticosteroid type (deflazacort vs prednisone/prednisolone) at baseline, and a subgroup of ambulatory/non-ambulatory subjects at study entry.

## 5.4. Clinical History

N/A.

## 5.5. Concomitant Medications and Procedures

Prior medications and concomitant medications will be coded using the World Health Organization Drug Dictionary (WHODRUG) dictionary dated 2017DEC01 into Anatomical-Therapeutic-Chemical (ATC) classification codes. The prior medications are defined as any medications that subjects started before the first dose date. Concomitant medications are defined as any medications that subjects took after/on the first dose date. The prior and concomitant medications will be summarized by ATC level 3 and preferred terms. The concomitant cardiac medications will be summarized similarly.

Specific attention will be focused on corticosteroid use. The numbers of subjects receiving/not-receiving corticosteroids at baseline or during the study, switching in different types of corticosteroids during the study, and duration of corticosteroid use during the study and by type will be summarized.

The prior and concomitant non-drug therapies will be defined similar to the prior and concomitant medications. They will be coded by MedDRA version 20.1 and summarized by SOC and PT.

## 5.6. Study Drug Exposure and Compliance

Study drug compliance will be assessed in terms of the percentage of drug actually taken relative to the amount that should have been taken during the study. Treatment duration (weeks) will be calculated as  $(\text{last dose date} - \text{first dose date} + 1)/7$ , if date of last study drug intake was not known:  $(\text{last visit date} - \text{first dose date} + 1)/7$ . The summary of the overall compliance and treatment duration will be represented for overall subjects and a subgroup of ambulatory/non-ambulatory subjects at study entry.

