7.2.4. End of Treatment

The patient will return to the clinical research facility at Week 144 (Visit 13) for the End-of-Treatment visit. If the patient discontinues prematurely (ie, before Week 144), and the procedures that would normally be performed at Week 144 should be performed as a Premature-Discontinuation Visit before the patient leaves the study. If the patient terminates the study early because ataluren is commercially available in that country then the patient does not need to come in for the 6-week Post-Treatment Follow-up Visit.

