7.2.5. Post-Treatment Visits

All patients who discontinue study drug, except patients switching to commercial ataluren, must return for a Post-Treatment Visit at the investigator site 6 weeks (± 7 days) after the last dose of study drug and the End of Treatment Visit, for final study-related evaluations. If the End-of-Treatment Visit occurs >6 weeks after the last dose of study drug, the Post-Treatment Visit does not need to be performed.

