Listings of death, serious AEs, AEs leading to discontinuation from treatment, and hepatic and renal AEs leading to special diagnostic evaluations will be provided.

The drug exposure adjusted TEAE incidence rate will be summarized by SOC and PT, where the incidence rate of the TEAE per 100 patient-year = (number of events/number of patient-years) \*100. The number of patient-years is defined as the sum of the number of days on study drug of all patients divided by 336. That is, a year is defined as 48 weeks.

In addition, the number of subjects with clinical laboratory abnormalities, abnormal vital signs, and abnormal electrocardiogram reported as TEAE will be summarized.

Non-serious TEAE will be displayed by SOC and PT. The common non-serious TEAE (subject frequency of  $\geq 5\%$ ) will also be displayed by SOC and PT.

Numbers of occurrence of serious TEAE and the numbers of occurrence of non-serious TEAE will be summarized by SOC and PT, separately.

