## 6. DATA HANDLING

### 6.1. Analysis Visits based on Visit Windows

Since some subjects had early terminations or unscheduled visits in during, the derived analysis visits will be generated by visit window defined as follows. For the 6 weeks post-treatment visit, assign AVISITN=14 and AVISIT=6-Weeks Post-Treatment.

Let Study day=assessment date –first dose date +1.

Study Day	AVISITN	AVISIT
Study Event='SCR' or < study day $\leq$ 1	1	Baseline
1 < study day $\leq$ 126	2	Week 12
126 < study day $\leq$ 210	3	Week 24
210 < study day $\leq$ 294	4	Week 36
294 < study day $\leq$ 378	5	Week 48
378 < study day $\leq$ 462	6	Week 60
462 < study day $\leq$ 546	7	Week 72
546 < study day $\leq$ 630	8	Week 84
630 < study day $\leq$ 714	9	Week 96
714 < study day $\leq$ 798	10	Week 108
798 < study day $\leq$ 882	11	Week 120
882 < study day $\leq$ 966	12	Week 132
966 < study day	13	Week 144

If there are more than 1 valid assessment within one visit window, the last one will be chosen as the analysis value.

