#### **6.4.2.2. Incomplete Stop Date**

The following rules will be applied to impute the missing numerical fields. If the date of the last dose of double-blind study drug is missing, replace it with the last visit date or data cut-off date if the subject is on-going. If the imputed stop date is before the start date (imputed or non-imputed start date), then the imputed stop date will be equal to the start date.

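### When the last dose date is unknown, SAP 5.6 ends treatment duration at the last visit without excluding the 6-week post-treatment visit, so about 6 drug-free weeks can be counted as treatment

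*SAP*

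**What the plan says.** SAP 5.6 defines treatment duration in weeks as (last dose date − first dose date + 1)/7. The fallback, "if date of last study drug intake was not known", has the same form with the last visit date in place of the last dose date. The SAP does not say which visits qualify and sets no upper limit.

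Protocol 7.2.5 requires boys who stop study drug to attend a "Post-Treatment Visit at the investigator site 6 weeks (± 7 days) after the last dose of study drug". Two groups are exempt. For a boy who leaves because ataluren is commercially available in his country, Protocol 7.2.4 says "then the patient does not need to come in for the 6-week Post-Treatment Follow-up Visit". The other exemption is in Protocol 7.2.5: "If the End-of-Treatment Visit occurs >6 weeks after the last dose of study drug, the Post-Treatment Visit does not need to be performed".

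The post-treatment visit counts as a study visit. Both schedules of events list it as Visit 14, after the Week 144 visit, and neither shows drug being dispensed at Visit 13 or 14. SAP 6.1 gives it its own analysis visit: "For the 6 weeks post-treatment visit, assign AVISITN=14 and AVISIT=6-Weeks Post-Treatment".

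For exposure-adjusted adverse-event rates, SAP 5.7.1 states: "The number of patient-years is defined as the sum of the number of days on study drug of all patients divided by 336". It does not say how those days are derived, or whether the 5.6 fallback applies to them.

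**The concern.** Treatment duration should measure time on drug. If the last dose date is missing and the boy came to Visit 14, his last visit is off drug by design, and the SAP 5.6 formula read literally counts the interval as treatment. The same happens, by more than 6 weeks, to a boy whose End-of-Treatment visit took place more than 6 weeks after he stopped.

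This is an open-label extension whose primary objective is long-term safety, so length of exposure is one of its main descriptive results. The relative distortion is largest for boys who stopped early. If the rate denominator in SAP 5.7.1 is built from the same durations, these boys also make the adverse-event rates look slightly lower than they are.

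**Working it through.** The plan states no exposure total or expected duration for this point, so there is no figure to reproduce. The check applies the SAP 5.6 formula with two different end dates.

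**Inputs from the documents**
- Duration formula and fallback: SAP 5.6.
- Post-treatment visit 42 ± 7 days after the last dose, that is 35 to 49 days: Protocol 7.2.5.
- Planned treatment up to 144 weeks: Protocol 6.2.1.
- A patient-year is 336 days: SAP 5.7.1.
- Upper bound of about 220 boys: SAP 3.4.
- Drug for 90 days supplied at each dispensing visit: Protocol 7.11.

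**Inputs assumed, because the documents give none**
- Share of boys with an unknown last dose date who attend Visit 14: 1% to 10%.
- Mean time on drug: 48 or 96 weeks.

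**Step 1: excess per affected boy.** With first dose F, true last dose L and last visit V, the fallback minus the true duration is (V − F + 1)/7 − (L − F + 1)/7 = (V − L)/7. With V at Visit 14 this is 42/7 = 6 weeks (35/7 = 5 to 49/7 = 7).

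**Step 2: relative overstatement for that boy.** This is excess divided by true duration.

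| True weeks | Weeks under fallback | Overstatement at 6 weeks | Range for 5 to 7 weeks |
|---|---|---|---|
| 12 | 18 | 6/12 = 50% | 42% to 58% |
| 24 | 30 | 6/24 = 25% | 21% to 29% |
| 48 | 54 | 6/48 = 12.5% | 10.4% to 14.6% |
| 96 | 102 | 6/96 = 6.3% | 5.2% to 7.3% |
| 144 | 150 | 6/144 = 4.2% | 3.5% to 4.9% |

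In SAP patient-years the excess is 42/336 = 0.125 per boy (35/336 = 0.104 to 49/336 = 0.146).

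**Step 3: effect on total exposure.** With share f affected and mean exposure m weeks, patient-years are inflated by f × 6/m.
- m = 96: 0.01 × 6/96 = 0.06%; 0.05 × 6/96 = 0.31%; 0.10 × 6/96 = 0.63%.
- m = 48: 0.01 × 6/48 = 0.125%; 0.05 × 6/48 = 0.63%; 0.10 × 6/48 = 1.25%.

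For 220 boys the added exposure is 220 × 0.01 × 0.125 = 0.275 to 220 × 0.10 × 0.125 = 2.75 patient-years. If the same days form the rate denominator, an event rate is multiplied by 1/(1 + inflation). At the extremes above it falls by 0.06% (m = 96, f = 1%) and by 1.23% (m = 48, f = 10%).

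**Step 4: the other direction.** A boy who stops attending has a routine treatment visit as his last visit, and he left it with up to 90 days of drug. Doses taken after that visit are not counted. For him the fallback can understate exposure by anything up to that supply.

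**The case against.** The strongest counter-argument is that the two conditions should seldom coincide. Visit 14 is scheduled from the last dose, so a site that books it normally knows the date. Protocol Section 9 requires the date of discontinuation in the source documents and the eCRF, and unused sachets are returned and recorded. Boys moving to commercial drug have no Visit 14. A programmer might also read *last visit* as the last treatment visit. All of this stands as a reason to expect a small effect. It does not change what the rule says, and the wording of SAP 5.6 includes Visit 14.

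A reader might be tempted by four stronger inferences, which the documents do not support.

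- **That the bias always lengthens exposure.** Loss to follow-up while still dosing works the other way, and the documents do not show which case is commoner.
- **That the adverse-event rates are necessarily too low.** SAP 5.7.1 does not say that its days on drug come from the 5.6 fallback. The link is plausible but unstated.
- **That SAP 6.4.2.2 spreads the same error.** Its sentence "If the date of the last dose of double-blind study drug is missing, replace it with the last visit date" belongs to the rules for incomplete stop dates of prior and concomitant medications. Nothing ties it to treatment duration.
- **That the window for treatment-emergent events would run to about 12 weeks after the true last dose.** SAP 5.7.1 anchors that window on the last dose and states no substitute date.

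**Conclusion.** The point holds as a narrow defect of wording. For a boy with an unknown last dose date who attends Visit 14, SAP 5.6 as written overstates treatment duration by about 6 weeks (5 to 7). It overstates by more if his last visit is an End-of-Treatment visit held later than that.

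The effect on the study's total exposure is probably very small: about 0.06% to 1.25% of patient-years if 1% to 10% of boys are affected and mean exposure is 48 to 96 weeks. Those shares and means are assumptions. Any effect on the adverse-event rates is of the same size, and arises only if the 5.7.1 denominator is derived in the same way. No safety conclusion should turn on it. The change is optional but inexpensive.

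**What to change.** In SAP 5.6, replace the fallback to the last visit date with: the recorded study-drug discontinuation date or, if that is also missing, the date of the last on-treatment visit (End-of-Treatment/Premature-Discontinuation or earlier; never post-treatment Visit 14), not later than the last dispensing date plus the 90 days of drug supplied. State in SAP 5.7.1 that days on study drug use this same duration. Report how many boys needed each step of the fallback.

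The cost is a short text change and minor programming, and total exposure becomes slightly smaller. The rule remains imperfect in two ways:
- A late End-of-Treatment visit can still bring in off-drug time. If a boy stops 7 days after dispensing and is seen on day 56, the 90-day limit does not bind and 56 − 7 = 49 days (7 weeks) still count.
- A boy lost to follow-up while dosing may still be under-counted.

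Reporting the number of boys concerned lets the reader judge whether either matters.
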